Aim 1: Repeated measure (Rm)-ANOVAs will determine whether PPI, MMN and ASSR significantly differ after MEM vs. PBO (Hypothesis 1). Primary variables for each EAIP, as well as exploratory "secondary" measures, are identified above. Based on a recruited sample of 88 total participants, we will have 80% power to detect effect sizes of $d = 0.35$ (small) using a Bonferroni corrected $\alpha = .05/3$ (2-tail). Heterogeneity of response will be characterized using variance components expressed as intraclass correlation coefficients (ICCs).

Aim 2: Linear mixed-effects models regressing change in ADAS-cog outcome scores (at 8, 16, and 24 weeks vs. baseline) onto a fixed effect of group defined by MEM sensitivity will test the hypothesis that patients exhibiting a larger "MEM effect" on EAIP measures will exhibit a larger positive clinical response to MEM. Groups will be defined by a median split of "MEM effect" (MEM minus PBO) on EAIP. Power was estimated using methods described by Hedeker et al. (25) solving for sample size with $\alpha = .05$ (2-tail), test-retest correlations of .50, and 5% attrition at each time point. A sample of 88 total participants provides us with 80% power to detect a medium effect of $d = 0.50$. The primary outcome will be chosen based on effect sizes obtained as part of Aim 1. In exploratory analyses, we will also examine group by time interactions using orthogonal polynomial contrasts. We will also predict change in clinical outcomes as a function of all four candidate biomarkers in order to create an optimal prediction equation. We will perform ROC curve analyses using EAIP MEM sensitivity values as continuous variables and predict clinical improvement after MEM as a discrete outcome (responders vs. non-responders) in order to determine the clinical utility of this approach defined in terms of sensitivity and specificity. Secondary analyses will also be conducted with biomarker groups defined as "MEM-sensitive vs. -insensitive" via specific thresholds for EAIP MEM sensitivity.

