Does Aim 2 depend on Aim 1? What if MEM does not significantly enhance EAIPs in the inclusive group of AD patients? While our strong *a priori* hypothesis is that MEM will significantly increase PPI, MMN and ASSR in AD patients, this prediction is based on findings in HS and SZ patients (29,44,65,99,107), and secondarily, from findings in rats (107). Conceivably, brain circuitries that mediate the EAIP response to MEM might be damaged in AD, and hence MEM effects on EAIP measures may be blunted and not reach statistical significance across the inclusive group of AD patients. Importantly, for testing H2, the key outcome of Aim 1 will be a *heterogeneous EAIP response to MEM*, since the ability to detect significant moderating effects of MEM sensitivity on clinical response in Aim 2 relies on the *shared variance* between EAIP MEM sensitivity on the one hand, and *clinical MEM sensitivity* on the other. Thus, neither the ability to test H2, nor its importance, is diminished by an absence of a statistically significant effect of MEM in AD patients in Aim 1. *In fact, a lack of MEM response in Aim 1 might be a particularly important (negative) predictor of MEM clinical sensitivity, precisely because it reflects AD-related damage to brain substrates required for MEM's therapeutic effects.*

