Why Mild-to-Moderate AD? This application is designed to test the hypothesis that, nested within a heterogeneous cohort is a subgroup that will be identified via the proposed EAIP measures as “MEM-sensitive”, and that this “enriched” subgroup will exhibit a strong positive clinical response to MEM (Fig. 1). MEM is FDA-approved for use in patients with moderate-to-severe AD; the efficacy of MEM at these middle and late stages of AD has been demonstrated in several studies, without the use of predictive biomarkers. *Testing our hypothesis (H2) will be most feasible in an AD population that is NOT maximally sensitive to MEM.* At the other extreme, patients with MCI do not appear to benefit from MEM (186); it is likely that in the present study design, a low baseline level of symptoms in MCI could obscure a positive clinical response, even among a biomarker-defined “sensitive” subgroup. While MEM is commonly prescribed to patients with Mild-to-Moderate AD, its benefits appear to be modest among cohorts that are not stratified by predictive biomarkers (eg. Cohen’s d in mild-to-moderate AD at 8 weeks = 0.3 (81)). We are thus proposing to test patients with mild-to-moderate AD, based on the expectation that such a cohort will include a subgroup of MEM-sensitive individuals, and that detecting a clinical response in these patients will be facilitated by the fact that baseline symptoms are within a dynamic range, i.e. neither at extreme “floor or ceiling” levels. Importantly, MEM is FDA-approved for use only in moderate-to-severe AD based on documented efficacy (**rather than any increased risk of adverse events in mild-to-moderate severity patients**). Thus, we anticipate that MEM use in Aim 2 will not incur any added risks to the well-being of the study participants.

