Why no “control” group? Two potential “control” groups are not included in this design. First, no parallel HS group is included to confirm the predicted effect of MEM on EAIP measures during laboratory testing. Because such findings in HS have already been reported by our group, and extended in various forms by other groups (discussed above), we view a re- replication as unjustifiable in terms of effort or cost, particularly because the outcome of HS testing would not directly alter the interpretation of the key results (prediction of clinical response in AD patients). Second, no parallel AD treatment group is proposed. Thus, it is conceivable that the EAIP response to MEM might reflect a degree of neuroplasticity or other biological characteristic within AD-relevant brain substrates, that is a *general predictor* of a positive clinical response to other drugs, eg. AChE-I’s, rather than a *specific predictor* of a therapeutic response to MEM. While we considered this possibility, we felt that the most cost-effective and biologically parsimonious approach was to test whether EAIP MEM sensitivity predicts clinical MEM sensitivity; a positive finding might justify studies in a future application, testing similar predictive value in combined regimens (MEM+AChE-I) as well as AChE-I monotherapy.

FOA-specific information: The use of MEM in AD has been the focus of many large multi-site studies; this application will not broadly address MEM’s therapeutic role, i.e. its mechanism of action, the role of NMDA in

AD pathogenesis, or the predicted optimal disease stage for MEM use. The focus of this application is to test the predictive value of EAIP MEM sensitivity on its therapeutic impact in AD. Justification for experimental parameters is provided above, including treatment dose, duration and target population; we do not propose fundamental studies of MEM's clinical effects, eg. pharmacodynamics, because these are well established, though we plan to store blood for future tests of potential predictive biomarkers. Our plans for future clinical development are described briefly above, and include: 1. Tests that include patients using combination regimens (MEM + AChE-I); 2. Tests with patients at earlier stages of illness; 3. Tests with other AD therapeutics for which an acute EAIP-based laboratory biomarker is available.

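### The primary H2 comparison of non-randomised EAIP groups has no baseline-severity covariate, and the ROC and prediction analyses have no severity-only comparator, so severity could inflate or mask the association and added value would not be shown

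*Combined protocol and SAP*

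**What the plan says.** **Primary H2 model.** Under Statistical tests for each hypothesis, Aim 2 uses linear mixed-effects models for ADAS-cog change "at 8, 16, and 24 weeks vs. baseline) onto a fixed effect of group defined by MEM sensitivity". The groups come from a median split of the MEM-minus-placebo effect on EAIP. Power is stated as 80% for d = 0.50 with 88 participants and two-sided alpha 0.05, assuming "test-retest correlations of .50, and 5% attrition at each time point". The section Sex as a biological variable adds sex as a grouping factor in all major analyses. No MMSE, CDR or baseline ADAS-cog covariate is named for this model.

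**Utility analyses.** The same Aim 2 paragraph plans a prediction equation from the four candidate biomarkers. It also plans ROC curves on EAIP values, "in order to determine the clinical utility of this approach defined in terms of sensitivity and specificity". No model based on baseline data alone is named for comparison.

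**Where baseline measures do appear.** The Secondary / Exploratory Analyses list baseline neuropsychological and outcome measures, which include the ADAS-cog, as possible moderators of the marker-outcome relation. The Specific Aims list demographic, clinical and baseline neuropsychological variables in the same role. MMSE of 10-22 is an entry criterion.

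**Stage and benefit.** Under Why Mild-to-Moderate AD? the plan says of moderate-to-severe disease that "the efficacy of MEM at these middle and late stages of AD has been demonstrated in several studies, without the use of predictive biomarkers". It calls the benefit in mild-to-moderate cohorts modest (d = 0.3 at 8 weeks) and states that "patients with MCI do not appear to benefit from MEM".

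**Stage and marker.** Under Does Aim 2 depend on Aim 1? the plan allows that "brain circuitries that mediate the EAIP response to MEM might be damaged in AD". It adds that a missing EAIP response might predict poor clinical response because it reflects such damage. The Significance section likewise reads a positive challenge as a sign that the circuitry is spared.

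**The concern.** The two H2 groups are formed by a measured characteristic, and Why no control group? confirms that there is no parallel treatment arm. Any difference in baseline severity between the groups passes straight into the contrast in ADAS-cog change, whether it acts through drug benefit or through natural decline. The plan itself gives reasons to think that severity may relate to the marker and to benefit.

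The exploratory moderator analyses do not close this gap. They ask whether the marker-outcome slope varies with a baseline measure. They do not adjust the primary test, and they do not measure how much the challenge adds to what is already known at baseline.

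Two things are at stake. The first is the meaning of the H2 result, positive or negative. The second is the practical claim. The plan envisages steering marker-negative patients towards other treatments, and the marker costs two full test days. An EAIP-only ROC cannot tell a marker that carries new information from one that partly stands in for severity.

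**Working it through.** **1. Reproduce the stated power.** Inputs from the Aim 2 paragraph: 88 participants, so 44 per median-split group; three visits; correlation 0.50; two-sided alpha 0.05; d = 0.50; 5% loss per time point. I take retention as 1, 0.95 and 0.9025 at weeks 8, 16 and 24, because the primary set is patients who complete week 8.

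The variance factor for the mean of three visits under compound symmetry is

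V = (1/9) × [1 + 1/0.95 + 1/0.9025 + 2 × 0.5 × (1/√0.95 + 1/√0.9025 + 1/√(0.95 × 0.9025))] = 0.702.

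The SE of the group difference is √(2 × 0.702 / 44) = 0.179 SD. Power is Φ(0.50/0.179 − 1.96) = 79.9%, so the plan's 80% reproduces.

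**2. Effect of leaving severity out.** Let r be the stage-marker correlation and b the standardised stage-outcome slope. Neither is in the documents, so **both are assumptions**. A median split on the marker separates the groups in stage by 2√(2/π) × r = 1.596r SD. The spurious shift in d is then 1.596 × r × b.

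- False-positive rate when true d = 0: Φ(shift/0.179 − 1.96) + Φ(−shift/0.179 − 1.96).
- Power when severity opposes a true d of 0.50: Φ((0.50 − shift)/0.179 − 1.96).

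| r / b (assumed) | Shift in d | False-positive rate | Power for d = 0.50, opposed |
|---|---|---|---|
| 0.1 / 0.1 | 0.016 | 5.1% | 77% |
| 0.2 / 0.2 | 0.064 | 6.5% | 69% (68.5%) |
| 0.3 / 0.3 | 0.144 | 12.7% | 51% |

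Stronger associations (0.5 / 0.4) would give 43% and 17%, but nothing in the documents points to values that large.

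**3. Effect of adjusting.** A simulation of 88 patients (3,000 runs per cell, no attrition) added baseline stage as a covariate. It covered r/b of 0/0.3, 0.2/0.2, 0.3/0.3, 0.5/0.3 and 0.5/0.4. The rejection rate under the null was 4.7-5.1%, and power for d = 0.50 was 79-84%. No extra patients were needed in these cells.

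**4. ROC.** Simulating a marker with no signal of its own, with the outcome split at its median and r = b = 0.3, gives an AUC of 0.54 for the marker and 0.64 for stage alone. The marker's figure is all stage.

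**5. How precisely could added value be measured?** With 44 responders and 44 non-responders, an AUC of 0.60 has SE 0.060, so the 95% half-width is 1.96 × 0.060 = 0.12. In simulation, I took a marker correlated 0.3 with outcome and independent of MMSE, with MMSE correlated 0.2-0.3 with outcome. The mean AUC gain was about 0.07-0.09 and the bootstrap interval was about 0.18-0.19 wide. The interval excluded zero in fewer than half of trials, although the marker truly added information.

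**The case against.** **The plan does consider baseline measures.** This is correct. A reader might infer that severity is ignored altogether, and the moderator lists show otherwise. The gap is confined to the primary H2 model and the ROC and prediction analyses.

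**Utility is defined as sensitivity and specificity, and both can be estimated.** Also correct. A reader might infer that clinical utility cannot be shown at all; the documents do not support that. What is missing is utility *added* to baseline severity.

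**The stage gradient is between populations.** This stands. The text compares MCI, mild-to-moderate and moderate-to-severe AD and gives no gradient within MMSE 10-22. The remark about damaged circuitry is conditional and contrasts AD with other populations. H2 also analyses ADAS-cog change in an all-treated cohort, which mixes benefit with natural decline, so neither the sign nor the size of a stage-outcome correlation follows from the text.

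**The masking story is not the plan's own.** A reader might combine greater benefit at later stages with a blunted EAIP response and infer that severity must hide a true effect. The plan's own reasoning runs the other way: damage lowers both marker and benefit. Masking is one possibility, not a documented expectation.

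**If reflecting damage is part of the mechanism, adjustment changes the question.** This is the strongest point. An adjusted estimate asks whether the marker predicts beyond severity; an unadjusted one asks whether it predicts. Reporting both answers the objection.

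**Scope.** FOA-specific information says the study will not broadly address matters such as the drug's mechanism of action "or the predicted optimal disease stage for MEM use". Adjusting for severity does not study optimal stage; it makes the group contrast interpretable. The award is a pilot, and the ROC work follows the text on exploratory analyses, which argues for a descriptive comparator and not a formal criterion.

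**Conclusion.** The point holds in a limited form. The powered H2 contrast is between non-randomised groups with no severity covariate, and no analysis measures what the challenge adds to baseline severity. The plan's own text makes severity a plausible influence on both marker and outcome, so H2 could be inflated or masked.

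The size is unknown, because every correlation used here is assumed. At 0.1/0.1 the bias is negligible (false-positive rate 5.1%, power 77%). It becomes material at about 0.3/0.3 (about 13%, or power of 51%). The power calculation itself reproduces and is not in question. Because adjustment costs almost nothing, the change is worth making despite this uncertainty.

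Adjustment would not replace a control arm. Without one, the design cannot separate a marker that predicts response to memantine from one that predicts course in general.

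**What to change.** In the Aim 2 paragraph of Statistical tests for each hypothesis:

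1. Pre-specify baseline severity as a continuous covariate in the H2 mixed model. Name the measure in advance: screening MMSE, already obtained for eligibility, or baseline ADAS-cog. Report the unadjusted estimate alongside the adjusted one.
2. For the ROC and the prediction equation, also fit a severity-only model and a severity-plus-EAIP model. Report the gain in AUC and in explained variance with confidence intervals. Treat this as descriptive and not as a pass/fail rule, given the imprecision at 88 patients.
3. Limit any statement about clinical utility to what that comparison supports.

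Cost: plan wording, one degree of freedom in the H2 model and one extra comparator model; no new data. The downside is that the apparent utility of the challenge may look less favourable.

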Test Day 2	15	Physical exam, EKG, audiometry Neuropsychological testing	VS q 30 min, VAS q 60 min 1130: Lunch	Break 1445: EEG (50 min)

Fig. 8. Schedule: A. 3 sessions over \approx 2 weeks. B. Screen Day: C-D. Test Days: Total test time \approx 80 min; vital signs (VS) and VAS ratings taken all day, and parameters are set to notify the on-site study MD.

Intervention: Within 1 week of completing EAIP testing, subjects are seen by their primary provider, for initiation of MEM therapy. Many but not all patients will be treated through the UCSD MARC and Medicine for Seniors Clinics, where they were recruited. MEM is initiated at 5 mg/d and titrated with 5 mg weekly increments. During this time, subjects / caregivers are contacted weekly by study staff to assess adherence. Intervention Week 1 will begin when dosing reaches 10 mg bid.

Fig. 9. Study flow chart. Screening, testing and dose titration take 5 weeks. Starting from full dose (10 mg bid), ratings are completed at weeks 8, 16 & 24. Final n = 88.

[figure not shown]
Outcome measures: At the end of Intervention Weeks 8, 16 and 24, subjects will be evaluated with the ADAS-cog, the NPI-Q and Geriatric Depression Scale.

Analytic strategy: This study is not designed to test whether MEM monotherapy leads to clinical gains in mild-to-moderate severity AD: **this has already been studied** in large, multi-site trials (3,14,79,81). Rather, this study will determine whether laboratory-based biomarkers **predict which patients will benefit most from a "therapeutic" trial of MEM**. This hypothesis can only be tested using patients who complete a nominally "therapeutic" trial. Based on previous findings (Fig. 7), we plan to include in our full analyses all subjects who complete at least 8 weeks of MEM monotherapy (10 mg bid). Dose adjustments are permitted during weeks 3-8, but subjects unable to tolerate 10 mg bid by the end of week 7 will be characterized as "incomplete

treatment" in the final analyses. Importantly, separate analyses will consider "incomplete treatment" patients, those who discontinue MEM use or add an AChE-I in testing H2, as described below.

Fig. 10. Schematized overview of study design.

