Sex as a biological variable: Sex will be included as a grouping factor in all major analyses; groups will be sex balanced as described in "Human Subjects". The PI was the first to report sex differences and menstrual cyclicity of PPI in HS (102), and some EAIP sex differences may persist into late life (48). No sex differences in **MEM effects** on PPI, MMN (99) or ASSR (65) were noted in our studies (Fig. 2).

Timeline (Table 2): Screening 114 subjects/57 mo. (2 subjects / mo.) is well within the capacity of our referral sources in the UCSD Memory and Geriatric Medicine Clinics, ADRC and affiliated community network (cumulative flow >>15 new AD patients/wk). Proposed EAIP testing rate (< 4 tests / mo.) is well within our capacity (typical rate 16 tests / mo.). Thus, subject recruitment and test rate should meet the demands of the proposed "N". EAIP methods are currently in use in our lab, so no new training, equipment or infrastructure is needed. At a rate of ≈1.5 completed subjects/mo., we will reach our target in 57 months, leaving 3 months for genotyping, data analysis and writing. Interim analyses at ≈6 months will confirm the fidelity of all measures and potentially adjust MEM test dose (see above), and at 36 months will guide a future NIA application.

Key benchmarks of success will include: 1. Recruitment and clinical and neurocognitive assessment of 88 individuals with Mild-to-Moderate AD (M:F ≈ 44:44). 2. Completion of two days of EAIP testing in study subjects, one week apart, in a double-blind, cross-over design using PBO vs. 20 mg MEM. 3. Titration of MEM to target dose (10 mg bid). 4. Repeated clinical and neurocognitive assessment after 8, 16 and 24 weeks of MEM treatment. 5. Completion of proposed analyses of EAIP and clinical data to test hypotheses, H1 and H2.

Potential Limitations:

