1. Recruitment: One concern is the possible difficulty recruiting sufficient numbers of individuals with mild-to-moderate severity AD. A strength of this application is its intimate ties to active AD clinics and ongoing studies with large samples of well-characterized older adults, many of who have been diagnosed with AD, through collaborations with the UCSD Memory Clinic and Geriatric Medicine Outpatient Clinic, the UCSD ADRC and its affiliated networks throughout San Diego. Recruitment needs for this application are ≈ 2 new subjects / mo. (see "Timeline" and Table 2), with a projected 10% attrition at screening, and 5% attrition at each of the subsequent points of study contact (EAIP testing, weeks 8, 16 and 24), based on past experience and ongoing studies. The target population (mild-to-moderate AD) is not a focus of most ongoing UCSD studies, which prioritize MCI and Pre-MCI subjects; thus, availability of AD patients for this application will support much higher recruitment needs if attrition exceeds projected rates.

2. EAIP measures in AD patients: Our published reports of MEM effects on EAIP measures involved HS and SZ patients, ages 18-55 (65,99). The present application proposes such measures in patients with mild-to-moderate severity AD, ages 50-70 y; thus, both diagnosis and age of the proposed cohort differ from our past experience, and may present unexpected challenges. Importantly, our laboratory group has published extensively on EAIP measures across the full lifespan (eg. ages 18-88: (16)), and in populations with severe dementia and behavioral disturbances (eg. Huntington's Disease (104)), and recently completed a study of EAIP measures in 20 patients with mild-to-moderate severity AD ([name], PI). Thus, neither the clinical symptoms nor age of the proposed cohort should limit the acquisition or interpretation of EAIP measures.

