3. Expertise: The PI was Co-Director of the UCSD GHPP Clinic for 10 years (serving patients with Huntington's Disease (HD) and Hereditary Ataxias), and has been a clinically active Board Certified Psychiatrist for 24 years. While he has never had a primary role in AD clinical research, the PI brings to Aim 1 over 30 years of studies of EAIP measures, including studies of MEM effects on EAIP measures in rodents, HS and patients with SZ, and EAIP studies in patients with HD, Tourette Syndrome and other brain disorders (100,104). He has published extensively on the development, validation, interpretation and conceptual implications of EAIP measures as biomarkers in HS and patient populations (cf. 60-3,108). Importantly, the PI has assembled a team with expertise in AD, its assessment and treatment, and the conduct of clinical trials in AD. This team includes active Co-I's of Drs. [name], [name], [name] and [name], who collectively have significant expertise in these areas (see Biosketches) as well as the active collaboration of the leadership of the UCSD ADRC (Drs. [name] and [name]) and ADCS (Drs. [name] and [name]) (see Letters).

Table 2. Projected screening and completion "n"					
Study Month	12	24	36	48	57
Screen	24	48	72	96	114
EAIP Tests	21	43	64	86	103
Wk 8 measures	20	40	60	81	98
Wk 16 measures	19	38	57	77	93
Wk 24 measures	18	36	54	73	88

Protection of Human Subjects

(1) The final subject population for the present application will include approx. 88 adults, ages 50-70, carrying a diagnosis of AD, mild-to-moderate severity (based on a Mini-Mental Status Examination (MMSE) score of 10-22. Rationale for selection of this level of AD severity is discussed in the Research Strategy. The representation of males and females will be roughly equal; sample size is based on power analyses described above. We anticipate that, in order to complete testing in 88 subjects, we will need to "consent" and screen approximately 114 subjects; the remaining subjects will be excluded based on specific screening results, or self-initiated study withdrawal.

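### Table 2 counts attrition but no follow-up time: at 2 screenings a month about 74 to 78 patients, not 88, have week-24 data at month 57, and the Aim 1 interim counts do not match the table

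*Combined protocol and SAP*

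**What the plan says.** - **Screening and finish date.** The Timeline section gives "Screening 114 subjects/57 mo. (2 subjects / mo"). It says that "we will reach our target in 57 months, leaving 3 months for genotyping, data analysis and writing", which implies a 60-month project. Resource Sharing also has experimental activity complete at month 57.
- **Table 2.** At month 57 it shows 114 screened, 103 EAIP-tested, and 98, 93 and 88 with week-8, week-16 and week-24 measures. The row that carries the 88 is "Wk 24 measures".
- **Time per patient.** The Fig. 9 caption says "Screening, testing and dose titration take 5 weeks", with ratings 8, 16 and 24 weeks after full dose is reached.
- **Attrition.** Potential Limitations, item 1 (Recruitment), gives 10% at screening and then "5% attrition at each of the subsequent points of study contact (EAIP testing, weeks 8, 16 and 24"), which is four 5% losses.
- **Interim looks.** The Interim Analysis section expects n = 18 for Aim 1 biomarker data at about 6 months and n = 54 at about 36 months.
- **Meaning of 88.** Fig. 9 calls it the final n. Protection of Human Subjects (1) says about 114 must be screened "in order to complete testing in 88 subjects". The Aim 1 power statement calls 88 the recruited sample, and the Aim 2 power statement allows a further 5% loss at each time point.

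**The concern.** A patient screened in month 57 cannot have week-24 data in month 57. If the table ignores elapsed time, the completion number and the finish date cannot both hold at the stated screening rate. The study would then either close follow-up with fewer week-24 assessments than planned, or run beyond the project period and use up the three months kept for genotyping, analysis and writing. Patients screened late would go through two EAIP test days and contribute no ADAS-cog follow-up by the stated finish, although drug is budgeted through week 24 for every subject. Week-24 data matter mainly for the secondary question of how durable the response is.

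The interim counts raise a separate doubt. They are attached to Aim 1 biomarker data but look like counts of week-24 completers.

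**Working it through.** **Inputs.** Screening at 2 per month to month 57 (Timeline). Screening loss 10% and 5% per later contact (Recruitment). Lead-in of 5 weeks (Fig. 9). One month = 365.25/12/7 = 4.348 weeks.

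**1. Reproduce Table 2.** Cell = 2 × month × 0.90 × 0.95^k, with k = 0 (EAIP), 1, 2, 3 (weeks 8, 16, 24) and no lag. At month 57 this gives 102.6, 97.5, 92.6 and 87.97, against 103, 98, 93 and 88. The other columns agree to within 2 subjects. The table therefore allows no elapsed time and applies three 5% steps. The move from 114 to 103 is the 10% screening loss alone. With the four steps in the text, 114 × 0.90 × 0.95⁴ = 83.6, so the text does not give 88 even without a lag.

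**2. Add the lag.** From screening, week 8 falls at 5 + 8 = 13 weeks = 2.99 months, week 16 at 21 weeks = 4.83 months, and week 24 at 29 weeks = 6.67 months. Replace month by (month − lag). For week 24 at month 57:

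- screened early enough: 2 × (57 − 6.67) = 100.7
- three steps: 100.7 × 0.90 × 0.95³ = 77.7
- four steps: 100.7 × 0.90 × 0.95⁴ = 73.8

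| At month 57 | Week 8 | Week 16 | Week 24 |
|---|---|---|---|
| Table 2 | 98 | 93 | 88 |
| With lag, three steps | 92.4 | 84.8 | 77.7 |
| With lag, four steps | 87.7 | 80.5 | 73.8 |

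Varying the lead-in from 4 to 7 weeks gives 77.0 to 78.0 (three steps) and 73.1 to 74.1 (four). If follow-up continues to month 60, week-24 counts are 82.3 and 78.2.

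**3. When are 88 completers reached at 2 per month?** Three steps need 88/(0.90 × 0.95³) = 114 screened, so month 57.0 + 6.67 = 63.7. Four steps need 88/(0.90 × 0.95⁴) = 120 screened, so month 60.0 + 6.67 = 66.7.

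**4. Late entrants.** Patients screened after month 57 − 2.99 = 54.0 have no week-8 visit by month 57: 2 × 2.99 = 6.0 patients. Of these, 1.8 × (2.99 − 0.46) = 4.6 would have finished EAIP testing, taking two weeks (0.46 months) from screening to the second test day.

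**5. Interim counts.** EAIP-tested by month T = 1.8 × (T − 1 to 2 weeks).

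- Month 6: 12 screened and 10.0 to 10.4 tested (9.5 to 9.9 with a further 5% loss), against 18. A count of 18 is reached at 18/1.8 + 0.46 = month 10.5.
- Month 36: 64.0 to 64.4 tested (60.8 to 61.2 with the further loss), against 54.
- Table 2's week-24 row reads 18 at month 12 and 54 at month 36, which suggests the wrong row was used, and for 18 the wrong month too.

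**6. Effect on Aim 2.** The primary set needs only 8 weeks at the target dose, and about 88 to 92 patients reach week 8 by month 57. Starting from 88, the power statement's own attrition leaves 88 × 0.95² = 79.4 to 88 × 0.95³ = 75.4, so 78 at week 24 is within what it already allows. As an illustrative lower bound, suppose only patients with week-24 data were analysed (three visits, compound symmetry, correlation 0.5, d = 0.5, two-sided 0.05). Power would be about 77% with 78 and 75% with 74, against 82% with 88.

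**The case against.** The strongest reply is that the conflict depends on which 88 is meant. If 88 is the number entering, as the Aim 1 power statement has it, the calendar holds with three steps: the 88th EAIP-tested patient is screened at 88/1.8 = month 48.9 and reaches week 24 at 48.9 + 6.67 = month 55.6. With four steps it is 88/1.71 + 6.67 = month 58.1, inside 60 months. That is correct, and it shows that the power statement asks for less than Table 2 promises. It does not rescue Table 2, Fig. 9 or Protection of Human Subjects (1), which all make 88 the number completing. Nor can Table 2 be read as eventual completers, because the Timeline and Resource Sharing sections both fix completion at month 57.

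Four further points have some force:

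- The shortfall is only about 0.3 to 0.4 screenings a month, and the Recruitment paragraph says that availability "will support much higher recruitment needs if attrition exceeds projected rates". This makes the fix cheap, but the numbers are still wrong as written.
- No rule stops follow-up of enrolled patients at month 57. The loss of late entrants therefore applies only if the stated finish is kept.
- The documents do not show whether three or four attrition steps are intended, so both are carried here.
- For the first interim look, the month rather than the count may be the error. Either way, 18 EAIP-tested patients at month 6 is impossible with 12 screened. The Timeline does not limit the 36-month look to Aim 1, but the Interim Analysis section does; with the lag, week-24 completers at month 36 would be 45, so 54 does not fit that reading either.

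The figure of about 1.5 completers a month is also sound as a steady-state rate (2 × 0.90 × 0.95³ = 1.54). The error is in applying it from month 0.

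**Conclusion.** The concern holds and is minor. At 2 screenings a month, the plan's own schedule gives about 78 patients with week-24 data at month 57 (three 5% steps), or about 74 (four), instead of 88. Reaching 88 takes until about month 64 or 67. The interim count of 18 at 6 months is impossible, and 54 at 36 months is not the EAIP-tested number. These results assume uniform accrual from month 0, the stated 5-week lead-in and the stated attrition rates; they barely move for lead-ins of 4 to 7 weeks. Primary Aim 2 power is not materially affected, and no stopping or dose rule rests on the counts of 18 and 54. What fails is the calendar and the promised week-24 number.

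**What to change.** 1. **Rebuild Table 2** with the 29-week lag and a single attrition scheme, and make the Recruitment text agree. At 2 per month with three steps, the rows for months 12/24/36/48/57 become: week 8, 15/36/56/77/92; week 16, 12/31/51/70/85; week 24, 8/27/45/64/78.
2. **Choose one target.**
   - (a) Keep 88 completers by month 57 and finish screening by 57 − 6.67 = month 50.3. This needs 114/50.3 = 2.27 screenings a month (three steps) or 120/50.3 = 2.39 (four). EAIP testing rises to about 4.1 to 4.3 tests a month. The sentence "Proposed EAIP testing rate (< 4 tests / mo.) is well within our capacity" then needs its figure edited; the typical rate given there is 16 a month.
   - (b) Keep 2 per month and restate the week-24 number at month 57 as about 78 (74 with four steps).
3. **Correct the Aim 1 interim counts** to about 10 at 6 months and about 64 at 36 months (61 with four steps). If 18 is the number wanted at the first look, move that look to about month 10.5.
4. **Define 88 once**, as entering or completing, in Fig. 9, the power statements, and Protection of Human Subjects (1).

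The cost is a table and text correction, plus a modest rise in the screening rate if (a) is chosen.
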